### **Human Subjects Protection**

#### **Informed Consent**

Written informed consent will not be obtained. This is a quality surveillance study and the risk of harm or discomfort that may occur as a result of taking part in this research study is not expected to be more than in daily life or from routine physical or psychological examinations or tests. The rights and welfare of study will be protected through the use of measures to maintain the confidentiality of study information. Study results will be presented or published in lieu of providing individual subjects additional information regarding the study. Patients will receive standard care (which following implementation in 2024 will include an EMS STEMI telehealth program). Data will be collected from paramedic records and the WFBH EMR. However, we are interested in publishing the findings of this implementation project. Therefore, this project meets the definition of human subjects' research.

Protocol version:

Template updated 9.24.14

**Request of a waiver of consent:**

- 1) *The research involves no more than minimal risk to participants.* The risk of harm or discomfort that may occur as a result of taking part in this research is not expected to be more than in daily life or from routine physical or psychological examinations or tests. Patients identified for participation in this study/quality surveillance will receive standard care. Administration of fibrinolitics is within the Scope of Practice and Protocols of Cherokee Tribal EMS. Therefore, the primary risk of participation is a breach in privacy and confidentiality.
- 2) *The waiver of informed consent will not adversely affect the rights and welfare of the participants.* The rights and welfare of participants will be protected through the use of measures to maintain the confidentiality of project information.
- 3) *The research could not practically be carried out without the waiver of informed consent.* To determine the effect of the telehealth program it must be utilized in a “real world” prehospital chest pain patient population. Performing informed consent would threaten the validity of this evaluation by introducing a significant selection bias. Furthermore, having paramedics obtain consent in the field is not practical or safe as this would prolong transport time and delay patient care, potentially leading to a worsening of clinical outcomes. In addition, ambulance transport for patients with acute chest pain is anxiety provoking. These patients are usually very concerned about having a heart attack and thus may not be in the appropriate frame of mind to ethically participate in informed consent during emergency transport.
- 4) *Participants will give verbal consent for both the conversation with the Physician and the use of the platform Pulsara.* Verbal consent for the use of the Pulsara platform will be obtained by the EMS provider. Once the physician is connected there will be a second verbal consent obtained for the conversation between the physician, EMS provider, and participant.
- 5) *Whenever appropriate, the subjects will be provided with additional information after participation.* Project results will be presented or published (if possible) in lieu of providing individual subjects additional information regarding the project.

**Confidentiality and Privacy**

Confidentiality will be protected by collecting only information needed to assess study outcomes, minimizing to the fullest extent possible the collection of any information that could directly identify subjects, and maintaining all study information in a secure manner. Access to individually identifiable private information will be limited to those people required to access this information in order to conduct this project. This includes project team members, IRB, adjudication committee, and data monitors.

The project database will contain a limited amount of individually identifiable private information in the form of whole date elements and medical record numbers. Each participant

Protocol version:

Template updated 9.24.14

will be assigned a unique sequential project identifier that will be linked to the participant's research record and source documents through a log housed locally. Access to the entire project database will be limited to project team members at WFBMC who are involved in the trial management activities, including project team members, the institutional review board (IRB), adjudication committee, and data monitors.

The full electronic database will contain the participant's unique project identifier, full date elements, and medical record numbers, but will otherwise be clean of identifiers. A key will link the project identifier to participants' personal identifiers. This key will be housed in the project binder or electronically in a secure project folder behind the medical center firewall. Access to data containing personal identifiers will be restricted to the project team members, IRB, adjudication committee, and data monitors. Data entry will be performed by trained research staff with valid confidentiality agreements.

Our project team members have experience implementing an electronic process using a secure web-based data entry system for data collection and participant tracking. For this proposal, we will leverage forms and processes already in existence, along with our existing web infrastructure, REDCap.

The web-based system allows research personnel to interact with data using web forms. The website will be designed with input from the research staff so that the workflow follows the protocol and is in line with how the quality surveillance will be conducted. Website activity will be monitored and audited for security purposes. Users may view detailed tracking and management information for each participant and/or by assessment time point. Once logged in, research staff may run reports, enter data into forms, and review and edit data. As data are entered, validations rules are applied before data are saved. Inconsistencies are noted for staff to resolve. Research staff can resolve many queries immediately, comparing the screen to the source, often cleaning the entire database record on the spot. For queries not immediately resolvable, warnings are displayed whenever the data entry screen is recalled. All access to the website will be logged and stored for auditing purposes.

Following data collection subject identifying information will be destroyed at the earliest opportunity, consistent with data validation and study design, producing an anonymous analytical data set. Data access will be limited to study staff. Data and records will be kept locked and secured, with any computer data password protected. No reference to any individual participant will appear in reports, presentations, or publications that may arise from the study.

### **Data and Safety Monitoring**

The principal investigator will be responsible for the overall monitoring of the data and safety of study participants. The principal investigator will be assisted by other members of the study staff.

### **Safety**

Protocol version:

Template updated 9.24.14

The safety plan for patients in this study is based on clinical experience with tenecteplase in completed and ongoing studies. The anticipated important safety risks for tenecteplase are outlined below. Please refer to the Tenecteplase Investigator's Brochure for a complete summary of safety information.

Several measures will be taken to ensure the safety of patients participating in this study. Eligibility criteria have been designed to exclude patients at higher risk for toxicities. Patients will undergo safety monitoring during the study, including assessment of the nature, frequency, and severity of adverse events. In addition, guidelines for managing adverse events are provided below.

Measures will be taken to ensure the safety of patients participating in this study, including the use of stringent inclusion and exclusion criteria and close monitoring of patients during the study. Administration of tenecteplase will be performed in a monitored setting in which there is immediate access to trained personnel and adequate equipment and medicine to manage potentially serious reactions.

### **Risks Associated with Tenecteplase**

Standard management of myocardial infarction should be implemented concomitantly with tenecteplase treatment.

Arterial and venous punctures should be minimized. Noncompressible arterial puncture must be avoided, and internal jugular and subclavian venous punctures should be avoided to minimize bleeding from the noncompressible sites. In the event of serious bleeding, heparin and antiplatelet agents should be discontinued immediately and treated appropriately. Heparin effects can be reversed by protamine.

### **Bleeding**

The most common complication encountered during tenecteplase therapy is bleeding. This may be either superficial from punctures or damaged blood vessels or internal bleeding at any site or body cavity. Bleeding may result in life-threatening situations, permanent disability, or death.

- The incidence of intracranial hemorrhage, especially symptomatic intracranial hemorrhage (sICH), in patients with AIS is higher in alteplase-treated patients than placebo-treated patients in published studies (for detailed information, see the alteplase United States Package Insert [USPI])

The type of bleeding associated with thrombolytic therapy can be divided into two broad categories:

- Internal bleeding, involving intracranial and retroperitoneal sites, or the gastrointestinal, genitourinary, or respiratory tracts
- Superficial or surface bleeding, observed mainly at vascular puncture and access sites (e.g., venous cutdowns, arterial punctures) or sites of recent surgical intervention

Protocol version:

Template updated 9.24.14

## **Management of Bleeding**

Patients will be excluded for the presence of conditions related to risks of bleeding.

Should an arterial puncture be necessary during the first few hours following tenecteplase therapy, use an upper extremity vessel that is accessible to manual compression is preferable. Pressure should be applied for at least 30 minutes, a pressure dressing applied, and the puncture site checked frequently for evidence of bleeding.

Each patient being considered for therapy with tenecteplase should be carefully evaluated and anticipated benefits weighed against potential risks associated with therapy.

Guidelines for management of patients who develop bleeding are provided in [Table 1](#).

In addition, any intracranial hemorrhage events (symptomatic and/or asymptomatic), if not already reported as an SAE by the investigator, are considered non-serious adverse events of special interest for this study and should be reported and submitted to the Sponsor.

## **Arrhythmias**

Coronary thrombolysis may result in arrhythmias associated with reperfusion. These arrhythmias (such as sinus bradycardia, accelerated idioventricular rhythm, ventricular premature depolarizations, ventricular tachycardia, etc.) are not different from those often seen in the ordinary course of AMI and may be managed with standard antiarrhythmic measures. It is recommended that anti-arrhythmic therapy for bradycardia and ventricular irritability be available when tenecteplase is administered.

## **Thromboembolism**

The use of thrombolytics can increase the risk of thromboembolic events in patients with high likelihood of left heart thrombus, such as patients with mitral stenosis or atrial fibrillation.

## **Cholesterol Embolization**

Cholesterol embolism has been reported rarely in patients treated with all types of thrombolytic agents; the true incidence is unknown. This serious condition, which can be lethal, is also associated with invasive vascular procedures (e.g., cardiac catheterization, angiography, vascular surgery) and/or anticoagulant therapy. Clinical features of cholesterol embolism may include livedo reticularis, “purple toe” syndrome, acute renal failure, gangrenous digits, hypertension, pancreatitis, myocardial infarction, cerebral infarction, spinal cord infarction, retinal artery occlusion, bowel infarction, and rhabdomyolysis.

## **Use with Percutaneous Coronary Intervention**

In patients with ST segment elevation myocardial infarction, physicians should choose either thrombolysis or percutaneous coronary intervention (PCI) as the primary treatment strategy for reperfusion. Rescue PCI if medically appropriate or subsequent elective PCI may be performed after administration of thrombolytic therapies; however, the optimal use of adjunctive antithrombotic and antiplatelet therapies in this setting is unknown.

Protocol version:

Template updated 9.24.14

## **Precautions**

Standard management of acute ischemic stroke should be implemented concomitantly with tenecteplase treatment. Arterial and venous punctures should be minimized. Noncompressible arterial puncture must be avoided and internal jugular and subclavian venous punctures should be avoided to minimize bleeding from the noncompressible sites. In the event of serious bleeding, heparin and antiplatelet agents should be discontinued immediately. Heparin effects can be reversed by protamine.

## **Re-administration**

Readministration of plasminogen activators, including tenecteplase, to patients who have received prior plasminogen activator therapy has not been systematically studied. Three of 487 patients tested for antibody formation to tenecteplase had a positive antibody titer at 30 days. The data reflect the percentage of patients whose test results were considered positive for antibodies to tenecteplase in a radioimmunoprecipitation assay, and are highly dependent on the sensitivity and specificity of the assay. Additionally, the observed incidence of antibody positivity in an assay may be influenced by several factors including sample handling, concomitant medications, and underlying disease. For these reasons, comparison of the incidence of antibodies to tenecteplase with the incidence of antibodies to other products may be misleading. Although sustained antibody formation in patients receiving one dose of tenecteplase has not been documented, readministration should be undertaken with caution.

## **Hypersensitivity**

Hypersensitivity, including urticarial/anaphylactic reactions, have rarely (< 1%) been reported after administration of tenecteplase (e.g., anaphylaxis, angioedema, laryngeal edema, rash, and urticaria). Monitor patients treated with tenecteplase during and for several hours after infusion. If symptoms of hypersensitivity occur, appropriate therapy should be initiated.

## **Drug Interactions**

Formal interaction studies of tenecteplase with other drugs have not been performed. Patients studied in clinical trials of tenecteplase were routinely treated with heparin and aspirin. Anticoagulants (such as direct oral anticoagulants, heparin and vitamin K antagonists) and drugs that alter platelet function (such as acetylsalicylic acid, dipyridamole, and GP IIb/IIIa inhibitors) may increase the risk of bleeding if administered prior to, during, or after tenecteplase therapy.

## **Drug/Laboratory Test Interactions**

During tenecteplase therapy, results of coagulation tests and/or measures of fibrinolytic activity may be unreliable unless specific precautions are taken to prevent in vitro artifacts. Tenecteplase is an enzyme that, when present in blood in pharmacologic concentrations, remains active under in vitro conditions. This can lead to degradation of fibrinogen in blood samples removed for analysis.

## **Management of Patients Who Experience Adverse Events**

Protocol version:

Template updated 9.24.14

## Management Guidelines

Guidelines for management of specific adverse events are outlined in Table 1.

**Table 1 Guidelines for Management of Patients Who Experience Bleeding**

Event	Action to Be Taken
Bleeding	

• In the event of serious bleeding, heparin and antiplatelet agents should be discontinued immediately and treated appropriately. Heparin effects can be reversed by protamine.

• Intramuscular injections and nonessential handling of the patient should be avoided for the first few hours following treatment with tenecteplase.

• Venipunctures should be performed and monitored carefully.

• Should an arterial puncture be necessary during the first few hours following tenecteplase therapy, it is preferable to use an upper extremity vessel that is accessible to manual compression. Pressure should be applied for at least 30 minutes, a pressure dressing applied, and the puncture site checked frequently for evidence of bleeding.

Refer to Sections 5.2–5.4 for details on safety reporting (e.g., adverse events) for this study.

## **SAFETY PARAMETERS AND DEFINITIONS**

### **Specification of Safety Variables**

Safety assessments will consist of monitoring and reporting adverse events (AEs) and serious adverse events (SAEs) per protocol. This includes all events of death and any study-specific issue of concern.

### **Adverse Events**

An AE is any unfavorable and unintended sign (including an abnormal laboratory finding), symptom, or disease temporally associated with the use of an investigational medicinal product (IMP) or other protocol-imposed intervention, regardless of attribution.

This includes the following:

- AEs not previously observed in the subject that emerge during the protocol-specified AE reporting period, including signs or symptoms associated with STEMI Care that were not present prior to the AE reporting period

Protocol version:

Template updated 9.24.14

- Complications that occur as a result of protocol-mandated interventions (e.g., invasive procedures such as cardiac catheterizations)
- If applicable, AEs that occur prior to assignment of study treatment associated with medication washout, no treatment run-in, or other protocol-mandated intervention
- Preexisting medical conditions (other than the condition being studied) judged by the investigator to have worsened in severity or frequency or changed in character during the protocol-specified AE reporting period

### **Serious Adverse Events**

An AE should be classified as an SAE if any of the following criteria are met:

- It results in death (i.e., the AE actually causes or leads to death)
- It is life-threatening (i.e., the AE, in the view of the investigator, places the subject at immediate risk of death. It does not include an AE that, had it occurred in a more severe form, might have caused death.)
- It requires or prolongs inpatient hospitalization
- It results in persistent or significant disability/incapacity (i.e., the AE results in substantial disruption of the subject's ability to conduct normal life functions)
- It results in a congenital anomaly/birth defect in a neonate/infant born to a mother exposed to the IMP
- It is considered a significant medical event by the investigator based on medical judgment (e.g., may jeopardize the subject or may require medical/surgical intervention to prevent one of the outcomes listed above)

### **METHODS AND TIMING FOR ASSESSING AND RECORDING SAFETY VARIABLES**

The investigator is responsible for ensuring that all AEs and SAEs that are observed or reported during the study, are collected and reported to the FDA, appropriate IRB(s), and Genentech, Inc. in accordance with CFR 312.32 (IND Safety Reports).

### **Reporting of Unanticipated Problems, Adverse Events or Deviations**

Any unanticipated problems, serious and unexpected adverse events, deviations or protocol changes will be promptly reported by the principal investigator or designated member of the research team to the IRB and sponsor or appropriate government agency if appropriate.

Expected adverse events in this project are limited to a potential loss of confidentiality. If a breach in confidentiality occurs, the event will be promptly reported to the IRB and other applicable regulatory agencies. The medical record will not be reviewed with the intent of detecting adverse events. In the event that an adverse event is identified during the chart review, the event will be recorded in the project records and IRB, sponsor, and other government agency event reporting criteria and guidelines will be followed.

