### **No**

Evidence exists that the AE has an etiology other than the tenecteplase (e.g., preexisting medical condition, underlying disease, intercurrent illness, or concomitant medication); and/or the AE has no plausible temporal relationship to tenecteplase administration (e.g., cancer diagnosed 2 days after first dose of tenecteplase).

Expected adverse events are those adverse events that are listed or characterized in the package insert (PI) or current Investigator's Brochure (IB).

Unexpected adverse events are those not listed in the PI or current IB or not identified. This includes adverse events for which the specificity or severity is not consistent with the description in the PI or IB. For example, under this definition, hepatic necrosis would be unexpected if the PI or IB only referred to elevated hepatic enzymes or hepatitis.

For patients receiving combination therapy, causality will be assessed individually for each protocol-mandated therapy.

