### **Exchange of Single Case Report with Genentech**

**[name]** will be responsible for collecting all protocol-defined Adverse Events (AEs)/Serious Adverse Events (SAEs) (related and not related to the product), pregnancy reports (including pregnancy occurring in the partner of a male study subject), other Special Situation reports, Non-Serious AESIs, Product Complaints (with or without an AE) where the patient has been exposed to the Product

It is understood and agreed that **[name]** will perform adequate due diligence with regard to obtaining follow-up information on these events, if they are incomplete.

In addition, reasonable attempts must be made to obtain and submit the age or age group of the patient in order to be able to identify potential safety signals specific to a particular population.

The **[name]** agrees to allow requests for follow-up information from Genentech, for instance, in order to fulfill regulatory obligations, or where the requested information is not already routinely covered by standard follow-up activities (e.g. clarification of data discrepancies, or to request typical confirmatory laboratory data or batch numbers for biologics and other advanced therapies). Genentech will not contact the reporter directly for such data, but will route all such requests for follow-up to the provided **[name]** contact. It is understood and agreed that **[name]** will be responsible for the evaluation of all the case safety reports originating from the study.

Transmission of these reports (initial and follow-up) will be either electronically via email or by fax to the following email address/fax number:

**[contact]

**Email:** [usds\\[contact]](mailto:[contact])

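### The protocol rules out reviewing records to find adverse events, yet promises to assess their frequency and to collect them all

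*Protocol*

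**What the plan says.** The protocol section *Reporting of Unanticipated Problems, Adverse Events or Deviations* contains three relevant sentences. On finding events: "The medical record will not be reviewed with the intent of detecting adverse events". On events that surface anyway: "In the event that an adverse event is identified during the chart review, the event will be recorded in the project records", with the usual reporting criteria then applied. On expectedness: "Expected adverse events in this project are limited to a potential loss of confidentiality".

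Other sections commit to more:

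- *Safety*: "Patients will undergo safety monitoring during the study, including assessment of the nature, frequency, and severity of adverse events".
- *Specification of Safety Variables*: "Safety assessments will consist of monitoring and reporting adverse events (AEs) and serious adverse events (SAEs) per protocol", and then "This includes all events of death and any study-specific issue of concern".
- *Exchange of Single Case Report with Genentech*: for patients exposed to the product, the responsible party "will be responsible for collecting all protocol-defined Adverse Events (AEs)/Serious Adverse Events (SAEs) (related and not related to the product".
- *Deaths*: every death in the adverse event reporting period is reported, whatever its attribution.

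On data sources, *Subjects selection criteria* and *Interventions and Interactions* say that participants are identified retrospectively and that data come electronically from EMS and WFBH records. *Sample Size* estimates that 35 patients will be treated with tenecteplase.

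**The concern.** An assessment of frequency, or a collection of all events, needs a method of looking for them. The protocol describes one data source and then says it will not be read for this purpose. Staff who follow the reporting section and staff who follow the supplier-exchange section would do different things with the same chart, and nothing says which is right.

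What is at stake is the safety record of a newly introduced treatment. The background section says this EMS service gave no fibrinolytics in the past four years. *Signal Management and Risk Management* makes the study sponsor primarily responsible for judging the study's benefit-risk balance. If events are recorded only when someone abstracting reperfusion times happens to see them, the count of treated patients is known while the count of harms is open-ended downward. A low event count could then not be told apart from a low detection rate.

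**Working it through.** No stated figure is at issue, so the check sets the sections side by side.

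**1. Is there a direct conflict on detection?** The reporting section excludes purposeful record review. *Safety* promises assessment of frequency, which cannot be obtained from chance sightings. The supplier-exchange section requires collection of all protocol-defined events, related or not. *Specification of Safety Variables* and *Deaths* require all deaths. The first of these is the plainest clash. The others state what must be collected without stating how, and the reporting section removes the obvious means.

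**2. Does another described route fill the gap?**

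- *Eliciting Adverse Event Information* relies on questions put to subjects when they are evaluated, but the protocol schedules no such evaluations.
- *Reporting Timeline for Applicable Events* counts 30 days from awareness, so it governs transmission and not discovery.
- *Management of Bleeding* asks for reports of intracranial haemorrhage even when asymptomatic, which a patient would not volunteer.
- *Data and Safety Monitoring* gives the principal investigator overall responsibility, *Confidentiality and Privacy* gives an adjudication committee and data monitors access to data, and *Design* mentions quality assurance. None of them prescribes a search for adverse events.

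The records are therefore the main place where the collection duty could be met.

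**3. Which way does the error run?** If the no-review sentence prevails, an event can be missed but the 35 treated patients are still counted, so recorded rates tend to be too low. If the collection duty prevails, the problem does not arise.

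**4. How large is it?** The protocol gives no capture rate and no rate for bleeding or intracranial haemorrhage, so the loss cannot be derived. For scale only, take the background section's 30-day STEMI mortality of nearly 8% and assume that it applies to the 35 treated patients:

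- Expected deaths = 35 × 0.08 = 2.8.
- Expected recorded deaths = 35 × 0.08 × c, where c is an assumed capture fraction.
- Probability of at least one recorded death = 1 − (1 − 0.08c)^35.

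| Assumed capture c | Expected recorded deaths | P(at least one recorded) |
|---|---|---|
| 100% | 2.8 | 0.946 |
| 75% | 2.1 | 0.885 |
| 50% | 1.4 | 0.760 |
| 25% | 0.7 | 0.507 |

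The capture fractions are assumptions, and the conclusion does not rest on them.

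**5. Expectedness.** The reporting section limits expected events to loss of confidentiality. The causality guidance under *Assessment of Adverse Events* says "Expected adverse events are those adverse events that are listed or characterized in the package insert (PI", or in the current Investigator's Brochure. *Bleeding* names bleeding as the most common complication of tenecteplase. If the insert or brochure lists bleeding, the same serious bleed is unexpected under one section and expected under the other.

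**The case against.** The strongest reply is that the conflict is narrower than a list of sections suggests. The safety-variables section speaks of monitoring per protocol, the supplier-exchange section of protocol-defined events, and the investigator's general duty covers events observed or reported. All of these can be read as compatible with passive capture. Events that come to light must still be recorded and reported. No objective, outcome or planned analysis concerns safety, so no estimate, test or sample size changes. The size of the loss is unknown.

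Much of this stands. It does not remove the clash with the promise to assess frequency. It also leaves unexplained how all events and all deaths are to be collected from records that are not read for them.

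Three stronger readings are tempting, and the protocol does not support them:

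- A reader might infer that adverse events will not be captured at all. The reporting section requires recording of those identified in chart review, so capture would be incidental, not absent.
- A reader might infer that the narrow definition of expected events also causes events to be lost. No such loss is shown. That section sends serious and unexpected events for prompt reporting, so counting a serious bleed as unexpected would favour its being reported. The sentence may also mean only the risk of data collection, as the consent-waiver section does when it names breach of privacy as the main risk of taking part. It does not say so, and this part is a matter of clarification.
- A reader might infer that the primary result is compromised. Reperfusion times and telehealth uptake do not depend on adverse event capture.

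**Conclusion.** The concern holds for event detection. The protocol gives incompatible instructions on whether records are searched for adverse events and does not say which governs. If the no-review sentence is followed, capture of bleeding, intracranial haemorrhage and death among the estimated 35 tenecteplase-treated patients depends on chance and tends toward undercounting, by an amount that cannot be derived. This rests on the retrospective records being the only described data source and on no evaluation visits being scheduled. The two definitions of expected events are a real inconsistency with no demonstrated effect on the number of events recorded.

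**What to change.** Delete the no-review sentence and state one ascertainment rule. The records already abstracted for reperfusion times are also reviewed, over a stated window, for AEs and SAEs in tenecteplase-treated patients, including at least death, intracranial haemorrhage and serious bleeding.

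If the sponsor prefers to limit active review to serious events, then *Safety*, *Specification of Safety Variables*, the supplier-exchange section and the quarterly listing of non-serious events under *Reporting Timeline for Applicable Events* must be reworded to match. Otherwise the conflict remains for non-serious events.

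Report, as a limit on ascertainment, the number of patients whose hospital course is not in the named records.

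Two clarifications can go in the same amendment. Restrict the confidentiality sentence to the risk of data collection and let the package insert or Investigator's Brochure definition govern tenecteplase-related events. Align *Management of Bleeding*, which treats intracranial haemorrhage as an event of special interest, with the list under *AEs of Special Interest*, which omits it.

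The cost is protocol wording and some extra abstraction in records already opened, with no new patients or procedures. The remaining weakness is incomplete hospital data: *Outcome Measure(s)* refers to more than one PCI center, while the only named hospital source is WFBH/WFUSM.
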